3.1.2.2 Study Intervention Phase

- Subjects assigned to wear the helmet will be asked to wear the Hövding Helmet during their daily lives with the following exceptions: swimming, bathing, driving or riding in a car, participating in activities with frequent changes in velocity such as sports, or handling children or infants.
- All 20 Subjects will complete a Seizure Calendar that will detail which how often and what type of seizures they are having
- During the time they are assigned to the helmet group, subjects will also record the number days that they wear the helmet.
- All 20 Subjects will complete a Seizure Questionnaire, which will be self-administered after the subject has a seizure to detail the circumstances of the seizure and any injuries sustained.
- During the time they are assigned to the helmet group, subjects helmet will complete a Helmet Deployment Questionnaire, which will be self-administered after the Helmet deploys to detail the circumstances of its deployment
- Those subjects able to do so will complete a Rivermead Post concussive scale which will be selfadministered 48 hours after their seizure if they sustain a head injury during a seizure or if the helmet deploys during a seizure, regardless of head injury.
- The study team will make monthly contact with each subject, to ask about seizure frequency, helmet deployment, and any other relevant information.
- If any subject seeks medical care for injuries during the trial, the study team will make every effort to obtain related medical records.
- Subjects will be instructed to contact the study team after they experience a seizure that results in a fall, or after a helmet has been deployed to schedule a follow-up visit.

3.1.2.3 Visit 2

After a helmet has been deployed or the subject experiences a seizure that results in a fall, subjects will be asked to return for visit 2. At this visit, the following study procedures will be performed:

- Medical History review
- Adverse Device Events review
- Helmet collection, if applicable
- If a subject with a VNS experiences a helmet deployment, their VNS will be interrogated at visit 2. If a problem is detected, appropriate clinical care will be provided.
- Dispense Helmet, if applicable
- Collect Seizure Calendar
- Collect Seizure Questionnaire
- Collect Helmet Deployment Questionnaire (if subject was assigned to wear a helmet at visit 1)
- Collect Rivermead Post Concussive Scale (for patients able to complete)
- Dispense Seizure Calendar
- Dispense Seizure Questionnaire
- Dispense Helmet Deployment Questionnaire (if subject is assigned to wear a helmet at this visit)
- Dispense Rivermead Post Concussive Scale (for patients able to complete)

At the end of this visit, subjects will switch groups. Those originally randomized to the helmet group will be assigned to the no helmet group, and those originally randomized to the no helmet group will be given helmets and assigned to the helmet group.

3.1.2.4 Visit 3

After a helmet has been deployed or the subject experiences a seizure that results in a fall, or at the end of six months of study participation, subjects will be asked to return for visit 3. At this visit, the following study procedures will be performed:

- Medical History review
- Adverse Device Events review
- Helmet collection, if applicable
- Collect Seizure Calendar
- Collect Seizure Questionnaire
- Collect Helmet Deployment Questionnaire (if subject was assigned to wear a helmet at visit 2)
- Collect Rivermead Post Concussive Scale (for patients able to complete)

3.2 Study Endpoints

3.2.1 Part 1 Endpoints

3.2.1.1 Primary Study Endpoints

The primary endpoint will be the rate of helmet deployment during staged falls.

3.2.2 Part 2 Endpoints

3.2.2.1 Primary Study Endpoints

• Differences in Rivermead Post Concussive Scale, Seizure Questionnaire, injury-related medical records, and qualitative subject report between subjects wearing helmets during a seizure, and subjects not wearing helmets during a seizure.

3.2.2.2 Secondary Study Endpoints

- Rates of helmet deployment (per event) during seizures associated with falls, and rates of helmet deployment (per day of use) not associated with seizure.
- Qualitative description of any adverse events.
- Differences in Rivermead Post Concussive Scale, Seizure Questionnaire, injury-related medical records, and qualitative subject report between subjects following a seizure in which the helmet deployed, and seizures in which the helmet was either not being worn or did not deploy

4 Study Population and Duration of Participation

4.1 Part 1

4.1.1 Inclusion Criteria

- 1. Age 18-60 at the time of enrollment.
- 2. Have neck circumference between 34 and 42 cm.
- 3. Can understand and provide written informed consent.
- 4. Must be competent to follow all study procedures.
- 5. Able to read, speak, and understand English.

4.1.2 Exclusion Criteria

1. Subject is currently pregnant

4.2 Part 2

4.2.1 Inclusion Criteria

- 1. Have at least one seizure every 6 months that might result in a fall (e.g. Generalized Tonic Clonic Seizure, Atonic Seizure, and/or Complex Partial Seizure resulting in a fall).
- 2. Has a seizure frequency of at least once per 2 months.
- 3. Be between ages 18-65 at the time of enrollment.
- 4. Have neck circumference between 34 and 45 cm
- 5. Must live in a home with electrical power supply.
- 6. If female and of childbearing potential, has negative pregnancy test at the beginning of the study and willing to use appropriate birth control for the duration of the study.
- 7. Subject or LAR can understand and sign written informed consent.
- 8. Subject or caregiver must be competent to follow all study procedures.
- 9.

4.2.2 Exclusion Criteria

- 1. Patient already wears a helmet for seizure safety.
- 2. Subject is pregnant, planning to become pregnant during the study, or is unwilling to use an appropriate form of birth control during the study.

4.3 Subject Recruitment

4.3.1 Part 1

We will distribute flyers around the Hospital of the University of Pennsylvania to recruit normal controls.

4.3.2 Part 2

Our primary method of recruiting subjects for this study will be reviewing the epilepsy database at the University of Pennsylvania, screening incoming clinic schedules, and referrals from attending neurologists. We will offer participation in the trial in addition to subjects' standard of care visits in the neurology office. We propose to recruit 20 subjects with Drug Resistant Epilepsy (DRE) who suffer from at least one seizure every 6 months that could be expected to result in a fall. Drug Resistant Epilepsy will be defined as subjects who have tried 2 or more antiepileptic medications and still having a seizure. Seizures that could be expected to result in a fall include generalized tonic-clonic seizures, drop seizure of any type, or a complex partial seizure with a fall. Prior history of head injury was removed as a criterion as well. We expect that 20 subjects will be sufficient in this preliminary study to determine safety and to suggest efficacy.

4.4 Duration of Study Participation

For Part 1, each subject's participation will last one day. Participation is complete when the subject falls. Subjects may be asked to repeat the fall if necessary. For Part 2, participation for enrolled subjects could last up to six months.

4.5 Total Number of Subjects

4.5.1 Part 1

Recruitment will end when 4 subjects are enrolled.

4.5.2 Part 2

Recruitment will end when approximately 20 subjects are enrolled, in order to document at least 5 evaluable seizures during helmet wear.

4.6 Vulnerable Populations:

N/A

5 Study Intervention

5.1 Description

The Hövding inflatable helmet is designed for cyclists as a collar with a deployable airbag that inflates when a sensor detects rapid changes in acceleration. When the cyclist encounters a crash, the airbag deploys and wraps the back and sides of the user's head in inflated nylon fabric which then slowly deflates after deploying. Its design is meant to be unobtrusive and fashion conscious to encourage greater compliance among the cyclist population; it is tested to a higher pounds per square inch standard than the current industry requirements for conventional bicycle helmets in the EU. Part 1 of this study, where normal controls (or dummies) are asked to fall from standing onto a padded surface while wearing the helmet, will address whether a fall outside of the context of cycling is sufficient for airbag deployment. If so, we will begin part 2 of the study.

6.1.1 Screening/Intervention

6.1.1.1 Visit 1

- Informed Consent
- Review Inclusion/Exclusion
- Demographics/Medical History
- Physical Exam
- Pregnancy Test only applicable if subject is female and of childbearing potential
- Subject training
- Fall subjects will be asked to fall on their sides onto a padded floor without breaking the fall with arms. If subject braces themselves and the helmet does not deploy, they may be asked to repeat the fall in the same controlled environment.

6.2 Part 2

Table 2: Schedule of Part 2 Study Procedures

	1	Intervention	2	Intervention	3
Informed Consent	Х				
Review Inclusion/Exclusion Criteria	Х				
Demographics/Medical History	Х				
Physical and Neurological Examination	Х		Х		Х
Pregnancy Test (if applicable)	Х	Xa	Xa	Xa	
Subject Training	Х		Х		
Assignment to treatment group	Х		Х		
Dispense Helmet	X^{d}		X^{d}		
Seizure Calendar	Xp	Х	Xbc	Х	Xe
Seizure Survey	Xp	Xd	Xbce	X ^d	Xe
Helmet Deployment Survey	Xp	Xd	Xbce	X ^d	Xe
Rivermead Post Concussive Scale	Xbd	Xd	Xbcde	X ^d	X^{ed}
Monthly Contact		X		Х	
Collect Helmet			X ^d		X^{d}
Adverse Device Effect (ADE) / Unanticipated ADE/ Unanticipated Problems Assessments		х		х	Х

^a Subsequent urine pregnancy tests may be administered at the investigator's discretion if there is reason to believe the subject may be pregnant.

^b dispensing

° collection

^d if applicable

6.2.1 Visit Schedule

6.2.1.1 Visit 1

- Informed Consent
- Review Inclusion/Exclusion
- Demographics/Medical History
- Physical and Neurological Exam
- Pregnancy Test only applicable if subject is female and of childbearing potential
- Subject Training
- Assignment to treatment group
- Dispense Helmet (if applicable)
- Dispense as applicable: Seizure Calendar, Seizure Survey, Helmet Deployment Survey, Rivermead Post-Concussive Scale

6.2.1.2 Study Intervention Part 1

- Seizure Calendar daily
- Seizure Questionnaire self-administered after a seizure
- Helmet Deployment Questionnaire self-administered after helmet deployment
- Rivermead Post-Concussive Scale self-administered by appropriate patients 48 hours after a seizure if the subject sustains a head injury during a seizure or if the helmet deploys during a seizure
- If subject seeks medical care for injuries during the trial, the study staff will collect any information available, including medical records.
- Study staff will contact subjects monthly

6.2.1.3 Visit 2

- Physical and Neurological Exam
- Pregnancy Test only applicable if subject is female and of childbearing potential
- Subject Training
- Assignment to treatment group (switch groups)
- Dispense or Collect Helmet
- Collect and Dispense new as applicable: Seizure Calendar, Seizure Survey, Helmet Deployment Survey, Rivermead Post-Concussive Scale
- Adverse Device Effects Collection

6.2.1.4 Study Intervention Part 2

- Seizure Calendar daily
- Seizure Questionnaire self-administered after a seizure
- Helmet Deployment Questionnaire self-administered after helmet deployment
- Rivermead Post-Concussive Scale self-administered by appropriate patients48 hours after a seizure if the subject sustains a head injury during a seizure or if the helmet deploys during a seizure
- If subject seeks medical care for injuries during the trial, the study staff will collect any information available, including medical records.
- Study staff will contact subjects monthly

6.2.1.5 Visit 3 (End of Study)

- Physical and Neurological Exam
- Collect Helmet (if applicable)

- Collect as applicable: Seizure Calendar, Seizure Survey, Helmet Deployment Survey, Rivermead Post-Concussive Scale
- Adverse Device Effects Collection

6.3 Subject Withdrawal

Subjects may withdraw from the study at any time without impact to their care. They may also be discontinued from the study at the discretion of the Investigator for lack of adherence to intervention or study procedures or visit schedules, ADEs, or due to a change in medical status that would make the subject ineligible, such as pregnancy. The Investigator may also withdraw subjects who violate the study plan, or to protect the subject for reasons of safety or for administrative reasons. It will be documented whether or not each subject completes the clinical study. Subjects who withdraw early will have one final visit to collect helmets (if applicable), calendars, and questionnaires, and to follow up regarding adverse events.

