Short Title	Inflatable Helmet for Seizures
IRB Number	824620
Methodology	Open Label Pilot Study
Study Duration	1 year
Study Center(s)	Single Center: University of Pennsylvania
	Part 1:
	To determine reliability in helmet deployment, as evidenced by
	deployment of the helmet during 4 staged falls with normal controls or dummies
	Part 2:
	Primary:
	• To compare rates and types of head injuries and post concussive
	symptoms in seizures resulting in falls occurring while the helmet was
	worn versus seizures resulting in falls occurring while the helmet was
Objectives	not being worn.
	Secondary:
	To determine helmet deployment in seizures versus helmet
	deployment in non-seizure situations.
	To understand adverse events associated with helmet deployment
	during seizures and otherwise.
	To compare rates and types of head injuries and post concussive
	symptoms from seizures leading to helmet deployment versus
	seizures in which the helmet did not deploy. This is contingent on
	there being episodes of helmet non-deployment.
Number of Subjects	Part 1: 4 Part 2: 20
Main Inclusion and	Part 1: Healthy controls
Exclusion Criteria	Part 2: Subjects who experience at least one seizure every 6 months who do not wear static solid helmets.
Investigational Product	Hövding Inflatable Helmet

Duration of administration (if applicable)	Part 1: 1 day Part 2: 6 months
Reference therapy	Static solid helmet
Statistical Methodology	Part 1: the number of times that the helmet deploys in normal controls falling from standing.Part 2: We will compare the rates of injury and post concussive symptoms in patients wearing a helmet during a seizure leading to a fall (independent of whether or not the helmet deployed), compared to patients not wearing a helmet during a seizure leading to a fall. We will also collect the number of days that subjects assigned to wear the helmet wore the helmet.
Safety Evaluations	Medical Record Review, Rivermead Post Concussive Scale, Qualitative Subject Report
Data and Safety Monitoring Plan	The Sponsor-Principal Investigator will conduct a self-assessment to review and evaluate study data and activities. The details of monitoring are included in the Data and Safety Monitoring Plan.

BACKGROUND AND STUDY RATIONALE

This study will be conducted in full accordance all applicable University of Pennsylvania Research Policies and Procedures and all applicable Federal and state laws and regulations.

1 Introduction

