This is a single-center, randomized, 2-way crossover study design. Using block randomization, enrolled participants will be assigned to first enter either the "helmet" or "no helmet" group following consent and confirmation that they meet all inclusion and none of the exclusion criteria. At the time of a seizure that results in a fall, subjects will be asked to fill out a questionnaire to help document the circumstances of the seizure and if any injuries occurred. If the patient seeks medical attention, their medical records will be reviewed afterwards. If a head injury is sustained, they will be asked to fill out the Rivermead Post Concussive scale 48 hours after their seizure in order to quantify their head injuries.² If the subject was wearing a helmet at the time of the fall and it deploys, or of the helmet deploys for any other reason, subject or their representatives will be asked to fill out an additional questionnaire detailing the circumstances of its deployment. After the helmet deploys, we will ask subjects to return their helmets to the University of Pennsylvania for Sponsor assessment. After this fall, or after any helmet deployment, subjects in both groups will be asked to return to the University of Pennsylvania for a study visit during which they will switch groups. If a subject is enrolled for 3 months without experiencing a seizure resulting in fall, they will be considered a screen fail.

During their participation in both groups, subjects will be asked to fill out a daily seizure calendar to help document the frequency of seizures and seizure types.

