8.3 Statistical Methods

Part 2:

- Will compare rates of injury and post concussive syndrome in falls where the helmet was being worn versus falls where the helmet was not being worn.
- Descriptive statistics will be collected on the proportion of days that subjects assigned to wear the helmet actually wear the helmet
- Descriptive statistics will also be collected on rates of helmet deployment (per event) during seizures associated with falls, and rates of helmet deployment (per day of use) not associated with seizure
- Will compare rates of injury and post concussive syndrome in falls where the helmet was being worn and deployed versus falls where the helmet was either not being worn or did not deploy

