8.3.2 Efficacy Analysis

8.3.2.1 Part 1

• Number of times the helmet deploys in normal controls (or dummies) falling from a standing position.

8.3.2.2 Part 2

- Number of days that subjects in the helmet group actually wore the helmet
- Compare the fraction of the time the device deployed during a seizure that resulted in a fall
- Compare the number of times the helmet deployed in a seizure vs. non-seizure event
- Compare seizures that trigger helmet deployment to those that do not trigger helmet deployment

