8.4 Subject Population(s) for Analysis

• All-randomized population: Any subjects in the study, regardless of whether they were assigned to wear the helmet, will be used for any analysis comparing helmet wear vs. no helmet wear.

9 Adverse Device Effects and Adverse Events

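### Removing subjects from the whole study for not wearing the helmet can distort the planned wear result and loses poor wearers' later falls

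*Combined protocol and SAP*

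**What the plan says.** On removal, Section 6.3 (Subject Withdrawal) states in part: "They may also be discontinued from the study at the discretion of the Investigator for lack of adherence to intervention or study procedures or visit". The exit is from the study, not only from the helmet. It is discretionary, and no wear threshold or timing is given. Section 6.3 then provides one final visit to collect the helmet, calendars and questionnaires and to follow up adverse events.

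On the intervention, Section 3.1.2.2 states: "Subjects assigned to wear the helmet will be asked to wear the Hövding Helmet during their daily lives with the following exceptions", followed by a list such as bathing and driving. In the helmet period, adherence to the intervention therefore means wearing the helmet.

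On wear as a result, three places plan it:
- Study Summary, Statistical Methodology: "We will also collect the number of days that subjects assigned to wear the helmet wore the helmet".
- Section 8.3: "Descriptive statistics will be collected on the proportion of days that subjects assigned to wear the helmet actually wear the helmet".
- Section 8.3.2.2, under Efficacy Analysis: "Number of days that subjects in the helmet group actually wore the helmet".

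On design, Section 3.1 states: "This is a single-center, randomized, 2-way crossover study design". The switch between groups is triggered by a seizure with a fall or by a deployment (Sections 3.1, 3.1.2.3 and 5.2).

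On the analysis population, Section 8.4 states: "Any subjects in the study, regardless of whether they were assigned to wear the helmet, will be used for any analysis" comparing wear with no wear. It does not say how discontinued subjects or their unobserved days are handled.

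**The concern.** The Introduction and Section 1.2 rest the case for this device on acceptability: patients refuse static helmets and might use this one. Low wear is therefore a finding the pilot should report. Section 6.3 makes the same low wear a reason to stop measuring it. The study is open label, and staff ask about wear time every month (Section 7.10), so the investigator will know who the poor wearers are.

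The ground also works on one side only. A subject cannot fail to wear a helmet while assigned to the no-helmet group. Non-adherence to procedures or visits, named in the same sentence, can arise in either period.

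Two things are at stake. One is the wear figure carried into the planning of the larger trial. The other is the record of later falls in subjects who wear the helmet little. Section 4.5.2 aims for only 5 evaluable seizures during helmet wear from about 20 subjects, so a few early exits matter.

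**Working it through.** The plan gives no expected wear rate or dropout, and Section 8.2 reads N/A, so there is no figure of its own to reproduce. From the documents: about 20 subjects (4.5.2) and a 3-month limit without a fall (3.1, 5.2). Assumed: a 90-day helmet period for everyone, good wearers wearing on 80% of days, poor wearers on 20%, and all poor wearers removed at day 30 or 60.

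**1. Main illustration: 14 good and 6 poor wearers, removal at day 30**
- True wear: (14×90×0.8 + 6×90×0.2)/(20×90) = (1008 + 108)/1800 = 1116/1800 = 62.0%.
- Pooled days after removal: (1008 + 6×30×0.2)/(1260 + 180) = 1044/1440 = 72.5%.
- Completers only: 1008/1260 = 80%.
- Mean of per-subject proportions: (14×0.8 + 6×0.2)/20 = 62.0%, unchanged.
- Mean days worn per subject: 1116/20 = 55.8 falls to 1044/20 = 52.2.
- Helmet-period days lost: 6×60 = 360, all from poor wearers.

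**2. Range over the assumed number of poor wearers and day of removal**

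| Poor wearers of 20 | True wear | Pooled, day 30 | Pooled, day 60 | Mean of subjects | Mean days worn: true | Day 30 | Day 60 |
|---|---|---|---|---|---|---|---|
| 4 | 68% | 75.4% | 71.4% | 68% | 61.2 | 58.8 | 60.0 |
| 6 | 62% | 72.5% | 66.7% | 62% | 55.8 | 52.2 | 54.0 |
| 10 | 50% | 65.0% | 56.0% | 50% | 45.0 | 39.0 | 42.0 |

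Completers only gives 80% in every row.

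**3. Simulation with varied wear**

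Each run had 20 subjects followed for 90 days, with wear propensity drawn from Beta(1.2, 1.0). Wear was reviewed at days 30 and 60, and a subject who wore the helmet on under 30% of the last 30 days was removed with a set probability. There were 4,000 runs per setting. With every flagged subject removed:

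| Wear over time | True | Pooled | Completers | Mean of subjects | Mean days worn |
|---|---|---|---|---|---|
| Constant | 54.5% | 61.5% | 67.9% | 54.1% | 49.0 to 46.3 |
| Declining | 34.8% | 41.4% | 47.7% | 36.1% | 31.3 to 28.7 |

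Over removal probabilities from 0.25 to 1, pooled days or completers only overstate wear by about 2 to 13 points. The mean of subjects moves by about -0.4 to +1.3 points.

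**4. What is lost, by sequence**

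A helmet-first subject removed for non-wear never enters the no-helmet period. A no-helmet-first subject keeps the no-helmet data and loses only the rest of the helmet period.

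**5. Does retention balance the falls comparison?**

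Section 8.3 compares falls by whether the helmet was actually worn. Take the step 1 values and further assume 90-day no-helmet periods, half the poor wearers helmet-first, and falls proportional to days.
- With removal, poor wearers supply 36/1044 = 3% of worn days. Their unworn days are 6×30×0.8 + 3×90 = 414, out of 414 + 252 + 1260 = 1926, or 21%. The gap is 18 points.
- With retention, they supply 108/1116 = 10% of worn days. Their unworn days are 6×90×0.8 + 6×90 = 972, out of 972 + 252 + 1260 = 2484, or 39%. The gap is 29 points.

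Retention recovers data but does not balance this comparison.

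**The case against.** The strongest reply is that no bias of known direction is shown. Removal is optional and has no threshold. Calendars that record helmet-free days (Section 7.5) are collected at the final visit, so wear before removal is kept. Section 8.4 keeps all randomized subjects, and Section 9.2 follows adverse events, which include injuries, to resolution or stabilization. Wear is descriptive and is not among the primary or secondary endpoints. The 90-day helmet period for everyone also does not fit the design: a period ends at the first fall or deployment, and a subject enrolled for 3 months without a fall becomes a screen fail.

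Much of this stands. A reader might infer that the rule necessarily inflates wear. The documents do not support that: they fix no estimator, the mean of per-subject proportions barely moves, and the count of days worn goes down. A reader might also infer that the rule is what makes helmet falls come from good wearers. That does not hold either. The selection comes from comparing falls by actual wear, and step 5 shows that the gap widens under retention.

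What the reply does not remove is that wear, seizure, fall and Rivermead collection stops for a reason that is itself a planned result and can arise only in the helmet period. Naming an all-randomized population does not supply data that were never collected.

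**Conclusion.** The point holds in a limited form. Section 6.3 permits removal from the whole study for non-wear, and no wear or fall data are planned after the final visit. This can distort the wear result. The proportion is inflated if days are pooled or only completers are used, nearly unchanged as a mean of per-subject proportions, and the count of days worn is lowered. The shift from 62% to 72.5% is an illustration on assumed wear rates, period length and removal, not an estimate for this trial.

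The loss of later falls from poor wearers, and of the entire no-helmet period for a helmet-first subject so removed, does not depend on the estimator. How often it would happen cannot be known from the documents. The confounding from comparing falls by actual wear is a separate matter that this change does not cure. The amendment is still worth making, because it is cheap now and follow-up that has been lost cannot be recovered.

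**What to change.** - **Section 6.3:** remove non-wear of the helmet, taken alone, as a ground for discontinuation from the study. Such subjects continue the calendar, questionnaires, Rivermead scale and monthly contact, and switch groups under the existing event-triggered rule, unless consent is withdrawn or another stated ground applies.
- **Section 8.3, with 8.3.2.2 and the Study Summary aligned:** state the wear estimator (pooled days or mean of per-subject proportions) and its denominator. Count assigned days not worn as zero wear. Report days after a stop for safety or an adverse device effect separately, so that medically required non-use is not read as refusal.
- **Reporting:** tabulate discontinuations by period, sequence and reason.

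The provisions on adverse device effects, safety, pregnancy and the 3-month limit are left unchanged. This change concerns data collection only. The cost is a short amendment and, for a few subjects, extra monthly contacts and calendars on existing forms.
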